#### 5.6.6 Digital Photography

Standardized total body photographs, regional photographs (e.g., torso, extremities, mouth) and close-up photographs of selected areas with active disease will be taken to monitor disease activity. The subject may decline photographs at any time during the study in instances where the subject is sensitive to being photographed. For additional instructions regarding Digital Photography, refer to the APG01 Manual of Procedures (MOP).

## 5.7 Concurrent Medications and Therapy

- If subjects are on prednisone at the Screening visit, subjects may continue to be treated with stable doses of prednisone not to exceed <25 mg/d until Week 12.
  - After Week 12, prednisone may be tapered at the discretion of the investigator, at a suggested rate of 5-10 mg decrease per month down to 10 mg/d, and then 1-5 mg decrease per month down to 0 mg/d.
  - Prednisone dose may be increased during the study for flares of pemphigus and for conditions that are not related to pemphigus based on the PI's clinical judgment. Increases in prednisone should occur only if absolutely necessary, and are discouraged for reasons other than pemphigus flares during the first 12 weeks of the trial. Stress doses of glucocorticoids may be used when clinically indicated.
- If subjects are on background immunosuppressive/immunomodulatory medications at the Screening visit, subjects should continue to be treated with stable doses of these agents until Week 12 including methotrexate  $\leq 25$  mg/week, mycophenolate mofetil  $\leq 3000$  mg/d, mycophenolic acid  $\leq 1080$  mg/bid, azathioprine  $\leq 200$  mg/d, cyclosporine  $\leq 5$  mg/kg/d, dapsone  $\leq 250$  mg/d and IVIG  $\leq 4$ mg/kg monthly.
  - After Week 12, changes in the above background medications may be made per the investigator's judgment. Thus, one medication may be stopped and another medication started. The dose of any of the medications must not exceed those specified above at any point during the study period.
- If a subject is having increased pemphigus disease activity at any point during the study, they will be treated according to the best clinical judgment of the investigator.
- If subjects are on topical agents at the Screening visit, subjects must continue to be treated with stable amounts (stable percentage and approximate volume) of these agents, including steroids and calcineurin inhibitors, until Week 12. After Week 12, the amount of the topical medications may be altered per the investigator's judgment.
  - Of note, topical medications must be held from the planned biopsy location for one week prior to each scheduled skin biopsy. Topical medications must be held 7 days to skin biopsy on Day 0 and may be resumed after the skin biopsy at Week 1. Topical medications must again be held for 7 days prior to the final biopsy at Week 12, and may be resumed after this procedure.

In addition, iron supplementation and medications for bone health are encouraged as follows:

- Daily multivitamin containing iron for at least 90 days after the blood donation visit
- Medications for bone health may include any or all of the following: calcium carbonate or citrate (up to 1500 mg/d of elemental calcium), vitamin D (up to 2000 IU/day), and bisphosphonates

In addition, the use of broad spectrum (ultraviolet A [UVA] and ultraviolet B [UVB]) sunscreen through the entirety of the trial is encouraged.

## 5.8 Prohibited Medications

Prohibited medications include:

- throughout the duration of the trial:
  - immunosuppressive medications other than those specified in Section 5.7, *Concurrent Medications and Therapy*
  - live attenuated vaccines
- 7 days prior to each skin biopsy at the site of the biopsy:
  - topical steroids, topical calcineurin inhibitors

### **5.9 Procedures for Monitoring Subject Compliance**

Subjects will not be self-administering any protocol-specified treatment. Therefore, their compliance will be monitored by their appearance for scheduled study visits, including acquisition of peripheral blood for expansion of Tregs, a subsequent single PolyTreg infusion, and follow-up visits for monitoring.

## **6 ASSESSMENT OF SAFETY AND EFFICACY**

### **6.1 General Assessments**

- Informed consent: written informed consent will be obtained before any study assessments or procedures are performed
- Demographics: date of birth, gender, self-identified race, self-identified ethnicity
- Medical History: Lifetime history of malignancy and family history of autoimmune disease. All other history should be from within 10 years prior to Screening Visit
- Comprehensive physical examination, at screening visit only
- Brief physical examination focused on participant's current complaints and clinical status
- Detailed Skin Examination
- Adverse Events. Participants will be assessed for adverse events at every visit
- Adverse Events Phone Assessment. Phone assessment for adverse events will be conducted at Day 2 and 3 and Weeks 3, 5 and 14
- Concomitant medications: Concomitant medications will be documented for 12 weeks prior to screening, and subsequently will be recorded at every visit
- Vital signs: height (at screening only), weight, temperature, heart rate, respiratory rate, sitting systolic blood pressure, sitting diastolic blood pressure will be assessed at every visit

### **6.2 Clinical Laboratory Assessments**

- Chest x-ray: unless chest x-ray has been performed within 3 months of the Screening visit and documented test results are available
- Serum pregnancy test
- Urine pregnancy test: Stat studies at week -2 and baseline visits

- Hematology: CBC with differential and platelets
- Chemistry: BUN, creatinine, AST, ALT, total bilirubin, direct bilirubin, alkaline phosphatase, albumin, sodium, potassium, chloride, and bicarbonate
- Infectious disease testing: HIV serology, HBsAg, anti-HBc Ab, anti-HBs Ag, and anti-HCV Ab (and HCV RNA if anti-HCV Ab test is reactive), unless performed within 3 months of the Screening visit and documented test results are available
- EBV & CMV IgG, unless performed within 3 months of the Screening visit and documented test results are available
- EBV & CMV viral load. See Section 5.6.1.3, *Epstein-Barr Virus* and Section 5.6.1.4, *Cytomegalovirus* for management guidelines
- TB testing: either a PPD or QuantiFERON®-TB Gold In-Tube test, unless performed within 3 months of the Screening visit and documented test results are available, or unless subject is known to have a positive or indeterminate test and has documentation of appropriate therapy
- Urinalysis with microscopic analysis
- Desmoglein 1/3 autoantibodies by ELISA
- Treg absolute count in peripheral blood

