### 4.2 Exclusion Criteria

Subjects who meet any of the following criteria are ineligible to participate in the study:

1. Initiation of systemic corticosteroid therapy, prednisone dose > 25 mg/d (or equivalent) or change in prednisone dose within 4 weeks prior to screening
2. Addition of a new medication, or change in the dose of any background medication used to treat any aspect of pemphigus within the timeframes listed below. Specifically:
  - a. methotrexate, mycophenolate mofetil, mycophenolic acid, azathioprine, cyclosporine or dapsone within the 6 weeks prior to screening or in the time between screening and study drug infusion

- b. IVIG within 12 weeks prior to screening or in the time between screening and study drug infusion (subjects on IVIG must be on stable dose for at least 12 weeks prior to screening)
    - c. treatment with cyclophosphamide within 12 weeks prior to screening or in the time between screening and study drug infusion
3. Doses of background medications at screening:
  - a. methotrexate > 25 mg/week
  - b. mycophenolate mofetil > 3000 mg/d
  - c. mycophenolic acid > 1080 mg/bid
  - d. azathioprine > 200 mg/d
  - e. cyclosporine > 2 mg/kg/d
  - f. dapsone >250 mg/d
  - g. IVIG > 4mg/kg IV monthly
4. Use of rituximab within the 12 months prior to screening
5. Change in dosing frequency, concentration, or applied surface area of topical steroids and/or topical calcineurin inhibitors within 2 weeks prior to screening
6. Paraneoplastic pemphigus
7. Pemphigus erythematosus
8. Pemphigus vegetans
9. IgA pemphigus
10. Drug-induced pemphigus
11. Blood donation within 10 weeks prior to baseline visit (Day 0)
12. Hemoglobin < 10 g/dl
13. White blood cell (WBC) count < 3,000/ mm^3 (equivalent to < 3 x10^9/L)
14. Absolute lymphocyte count < 800/mm^3 (equivalent to < 0.8 x10^9/L)
15. Absolute neutrophil count < 1,500/mm^3 (equivalent to < 1.5 x10^9/L)
16. Platelets < 100,000/mm^3 (equivalent to < 100 x 10^9/L)
17. Liver function test (aspartate aminotransferase [AST], alanine aminotransferase [ALT], or alkaline phosphatase [ALK]) results that are ≥ 2 times the upper limit of normal (ULN)
18. Direct bilirubin > ULN
19. End stage renal disease (estimated glomerular filtration rate [eGFR] < 20 ml/min/1.73m^2 using the CKD-EPI equation [59])
20. At or within three months of screening:

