  - a. positive QuantiFERON®-TB Gold test or positive purified protein derivative tuberculin skin test (PPD) (>5mm induration, regardless of Bacille Calmette Guerin [BCG] vaccine administration) unless completion of treatment has been documented for active TB
  - b. an indeterminate QuantiFERON®-TB Gold test unless followed by a subsequent negative PPD or negative QuantiFERON®-TB Gold test as well

as a consultation with and clearance by local infectious disease (ID) department

21. Recent or ongoing active bacterial, viral, fungal, or opportunistic infections requiring systemic anti-infective therapy
22. Evidence of current or prior infection with human immunodeficiency virus (HIV), hepatitis B (as assessed by HBsAg and anti-HBc Ab) or hepatitis C (as assessed by anti-HCV Ab)
23. Detectable circulating EBV or CMV genomes or active infection
24. Chronic infection that is currently being treated with suppressive anti-infective therapy, including but not limited to tuberculosis, pneumocystis, CMV, herpes zoster, and atypical mycobacteria, with the exception of historical orolabial or localized cutaneous herpes simplex infections treated with suppressive anti-viral therapy
25. Receipt of a live-attenuated vaccine within 12 months prior to screening
26. Concomitant malignancies or a history of malignancy, with the exception of completely treated basal cell carcinoma of the skin
27. Pregnancy
28. Lactating or breastfeeding
29. Unwilling or unable to use reliable method(s) of contraception (as described in Section 5.6.3, *Reproductive Risks*)
  - a. For females of child-bearing potential, from four weeks prior to Day 0 through 1 year after Treg dosing
  - b. For males, from the day of Treg infusion (baseline visit) to three months after Treg infusion
30. Use of an investigational therapeutic medication, or other biologic medications except rituximab, within the past 90 days, or 5 half-lives prior to screening, whichever is greater
31. Concomitant medical condition that places the subject at risk by participating in this study, including but not limited to:
  - a. another severe, systemic autoimmune disease or condition (besides pemphigus) requiring systemic immunosuppressive therapy (e.g., rheumatoid arthritis, SLE, systemic sclerosis, primary Sjorgen's syndrome, primary vasculitis, psoriasis, multiple sclerosis, ankylosing spondylitis, and inflammatory bowel disease), or

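### Section 6.2 waives the screening TB test for a treated indeterminate result of any age, so a subject whose result is over three months old can be infused with no negative TB test

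*Combined protocol and SAP*

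**What the plan says.** Section 6.2 (Clinical Laboratory Assessments) asks for a TB test at screening and gives two ways out of it. The first is limited in time: "either a PPD or QuantiFERON®-TB Gold In-Tube test, unless performed within 3 months of the Screening visit", with the result documented. The second is not: the test is also dropped "unless subject is known to have a positive or indeterminate test and has documentation of appropriate therapy".

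Section 4.2, exclusion 20, sets the entry standard. It opens with a time window: "At or within three months of screening". Inside that window:

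- Under 20a, a positive result excludes "unless completion of treatment has been documented for active TB".
- Under 20b, what excludes is "an indeterminate QuantiFERON®-TB Gold test unless followed by a subsequent negative PPD or negative QuantiFERON®-TB Gold test", and the negative retest must be accompanied by "as a consultation with and clearance by local infectious disease (ID) department".

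Table 6.1 schedules TB testing at the Screening visit only. Its footnote B covers rescreening and concerns earlier negative tests, so it does not limit the second waiver.

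**The concern.** Two sections set different TB standards for the same subject. For an indeterminate result, Section 6.2 accepts treatment as a reason not to test again, whereas 20b gives treatment no role and asks for a negative retest and specialist clearance. The stricter standard is tied to a three-month window and the waiver is not, so an older treated indeterminate result meets the waiver and falls outside the exclusion.

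What is at stake is a safety check at entry. Subjects on background immunosuppressants are to stay on stable doses until Week 12 (Section 5.7). Section 1.5.2.2 says it is unknown whether the infused cells alter protective immunity. Because TB testing is not scheduled again, a waived test is not made up later.

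**Working it through.** The plan gives no figure on this point and no arithmetic applies. The check is to trace each TB history through Section 6.2 and then through exclusion 20.

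**Indeterminate results**

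1. *Within three months of screening, treated.* Section 6.2 may waive a new test, but the known result lies inside the window. 20b applies in full: negative retest and clearance. No gap.
2. *Older than three months, not treated.* Neither waiver applies, so the subject is tested at screening and exclusion 20 acts on the new result. If it is negative, the subject enters. Clearance is not required, because the old indeterminate result is outside the window.
3. *Older than three months, treated, later negative test and clearance on record.* The substance of 20b is met. No gap.
4. *Older than three months, treated, never followed by a negative test.* Section 6.2 waives the test. No result lies inside the window, so 20b is not triggered. The subject can be infused with no negative TB test.

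Cases 2 and 4 show the anomaly most clearly. Of two subjects with an old indeterminate result, the untreated one must be retested and the treated one need not be.

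**Positive results older than three months**

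5. *Not treated.* No waiver; the subject is tested and exclusion 20 acts.
6. *Completed treatment for active TB, documented.* 20a would exempt this subject at any date. Same outcome under both sections.
7. *Treatment documented but not completed.* 20a's standard is not met. The waiver applies only if a site regards such treatment as appropriate, a term that Section 6.2 does not define.
8. *Completed treatment for latent TB.* The waiver applies. 20a names active TB only, so as worded it would exclude the same subject if the positive result were recent.

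**Other safeguards**

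- Exclusion 21 covers "Recent or ongoing active bacterial, viral, fungal, or opportunistic infections requiring systemic anti-infective therapy", and exclusion 24 covers chronic infection, TB included, under current suppressive treatment. Between them they catch most therapy still under way. They do not reach treatment that ended in the past.
- Exclusions 31c and 31d depend on the investigator's opinion.
- An x-ray is part of screening ("Chest x-ray: unless chest x-ray has been performed within 3 months of the Screening visit"), but no exclusion criterion names an x-ray finding.

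None of these supplies the missing negative test in case 4.

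**The case against.** The strongest reply is that the gap is close to empty. Documented appropriate therapy implies that a clinician has already dealt with the result. The exclusions for active and currently treated infection, the investigator's judgement and the chest x-ray remain. Section 1.5.2.1 calls the product's infection risk minimal in theory, and Section 5.6.1 asks for close monitoring afterwards. All of this stands, and it is why the point is minor. It does not restore the retest that 20b treats as necessary for an indeterminate result.

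Several stronger readings are tempting, and the documents do not support them:

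- *Any treated result older than three months escapes exclusion 20.* Not so. Cases 3 and 6 meet the standards of exclusion 20 on their own terms.
- *The waiver lets in subjects who stopped treatment early.* This needs a strained reading of appropriate therapy. The wording is loose, but abandoned treatment does not naturally fit it.
- *Completed latent-TB treatment is a loophole in Section 6.2.* The oddity lies in 20a's restriction to active TB, and nothing in the documents shows harm from admitting such a subject.
- *Sites will decide differently on the same history.* Read literally, the outcome turns on the test date and is the same everywhere. Variation between sites can arise only through the undefined word for therapy.
- *The waiver alone removes infectious disease clearance.* Case 2 shows that the three-month window already does so for untreated subjects with an old indeterminate result.

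**Conclusion.** The point holds for one history: an indeterminate result more than three months before screening, treated, with no later negative test. Section 6.2 and exclusion 20b are then inconsistent, and the subject can be infused without a negative TB test. For positive results the finding is smaller: the waiver's wording is looser than 20a's documented-completion standard and should match it.

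The size is small. Section 3.1 caps the trial at twelve infused subjects. The documents give no frequency for these histories, so no expected number is offered. No endpoint, analysis or sample-size statement changes. The conclusion rests on reading the opening window of exclusion 20 literally, so that it governs both 20a and 20b, and on there being no separate instruction to apply 20b to older results; none appears in the protocol.

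**What to change.** 1. In Section 6.2, delete *or indeterminate* from the second TB waiver. These subjects are then tested at screening and exclusion 20 acts on the new result: a negative admits, a positive goes to 20a, and an indeterminate goes to 20b.
2. In the same waiver, replace the appropriate-therapy condition with 20a's standard of documented completion of treatment, in identical words in both places. While aligning them, state whether completed treatment for latent TB counts, since 20a at present names only active TB.

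The first change restores the test but not infectious disease clearance. A negative retest would admit the subject, as it already does for any other subject with an old indeterminate result. If the sponsor also wants clearance, 20b must say that it applies to any prior indeterminate result, whatever its date.

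The cost is a small wording amendment to Sections 4.2 and 6.2 and an occasional repeat of a TB test already in the screening panel. Nothing in the statistical plan needs to change.

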### 6.3 Disease-Specific Assessments

- Skin biopsy for histopathology and direct immunofluorescence. Not required if results are documented prior to screening (see Section 4.1, *Inclusion Criteria* for details)
- Pemphigus Disease Area Index (PDAI): see Section 15.1, *PDAI*
- Skindex-29: see Section 15.2, *Skindex-29* [62, 63]
- PGA: see Section 15.3, *Patient's Global Assessment*
- PhGA: see Section 15.4, *Physician's Global Assessment*
- Digital photography: see Section 0, *Digital Photography* for details on types of photographs as well as adjustments for subject consent

### 6.4 Study Procedures

- Blood donation: approximately 400 ml will be collected into a blood bag
- PolyTreg infusion: the Baseline and Day 1 visits are both a part of the 24-hour observation hospitalization for the PolyTreg infusion (see Section 5.3.2, *Administration* for details)
- Specimen collection for mechanistic studies
  - Skin biopsies: Anatomic location and disease activity will be recorded for each biopsy site

- See Section 5.6.5, *Skin Biopsies*, 5.7, *Concurrent Medications and Therapies* and 5.8, *Prohibited Medications* for information on use of topical agents prior to skin biopsies
- See Section 5.6.5, *Skin Biopsies* for the considerations to determine location of the biopsies as well as procedural steps to minimize discomfort and scarring
- See Section 6.5, *Mechanistic Assessments* for information on the studies that will be conducted on these biopsies
- Blood: Sodium heparin (green top) tubes

## 6.5 Mechanistic Assessments

These mechanistic studies are designed to demonstrate the presence, persistence, and function of adoptively transferred Tregs in the blood and skin. Functionally analyzing both the adoptively transferred Tregs as well as endogenous T cell subsets in both the blood and skin enables comparison of the influence of adoptively transferred Tregs on the systemic immune system as well as on the local immune milieu in inflamed tissue. The following mechanistic studies will be performed: (i) mass spectrometry of transferred  $^2\text{H}_2$ -labeled Tregs in blood and skin and/or TCR sequencing to demonstrate the presence and assess the persistence of adoptively transferred Tregs; (ii) functional immunoflow cytometry on blood and skin to assess how transferred Tregs influence the cellular infiltrate and cytokine expression both systemically and in the target tissue; and (iii) whole transcriptome RNA-sequencing to assess gene expression changes in skin after Treg adoptive transfer.

### 6.5.1 Treg Tracking by Stable Isotope Labeling

[figure not shown]
APG01 relies on transferring PolyTregs that have been expanded hundreds-of-fold *in vitro*, which would be indistinguishable from endogenous Tregs by standard surface markers. However, because the cells are being expanded *ex vivo*, it provides a unique opportunity to label the cells prior to infusion to monitor engraftment and persistence of the administered PolyTregs. For over a decade, the Hellerstein group [64, 65] and others using their techniques, have applied stable isotope labeling with mass spectrometric analysis to measure the replication of murine and human cells *in vitro* and *in vivo*. Importantly, stable isotopes are non-radioactive and non-toxic, and they have been safely used as cellular, molecular, and metabolic markers in patients and healthy controls for more than six decades.

APG01 will label Tregs from pemphigus patients with deuterium by including the  $^2\text{H}_2$  label in the culture medium during the entirety of the expansion phase *in vitro* (Day 0 to Day 14) prior to infusion in the subject. In this technique, the  $^2\text{H}_2$  label is incorporated into the deoxyribose (dR) moiety in replicating DNA via the *de novo* synthesis pathway. Based on data from *in vitro* labeling studies, it is expected for 60% of purine deoxyribonucleosides in DNA strands to be labeled by deuterium at the time of infusion. After infusion, both PBMCs and single cell suspensions from skin biopsy specimens will be isolated and stored at time points as shown in Table 6.1, *Schedule of Events*. DNA prepared from these samples will be analyzed by gas chromatography-mass spectrometry in order to detect isotopic enrichment of the purine deoxyribonucleosides (deoxyadenosine [dA] or deoxyguanosine [dG]) [64, 66]. This method will identify infused Tregs in the systemic circulation and in the target tissue unequivocally. Based on estimates of the number of Tregs in the body ( $\sim 1 \times$

$10^{10}$ ),  $1.0 \times 10^8$  and  $2.5 \times 10^8$  transferred autologous Tregs in cohorts 1 and 2, respectively, will represent between 2.5% and 10% of total Tregs. Preliminary studies in patients with T1DM have confirmed that this method is capable of detecting transferred Tregs in the blood (see Figure 9). Based on these calculations, deuterium labeling is predicted to be detectable for at least four divisions of the administered Tregs. This method of detection should be especially advantageous at early time points (up to 28 days) post-infusion, prior to significant division and/or loss of Tregs. Importantly, between  $3 \times 10^6$  and  $5 \times 10^6$  live cells will be isolated from a single 4 mm punch biopsy of affected skin. Approximately 3-5% of these cells are Tregs, enabling a sample between  $9 \times 10^4$  and  $1.5 \times 10^5$  Tregs, which is well within the sensitivity of this assay [67].

